9.3 Annual safety report

In addition to the expedited reporting of SUSARs, the sponsor will submit, once a year throughout the clinical trial, a safety report to the accredited METC, competent authority, and competent authorities of the concerned Member States. This safety report consists of:

- a list of all suspected (unexpected or expected) serious adverse reactions, along with an aggregated summary table of all reported serious adverse reactions, ordered by organ system, per study;
- a report concerning the safety of the subjects, consisting of a complete safety analysis and an evaluation of the balance between the efficacy and the harmfulness of the medicine under investigation.

9.4 Follow-up of adverse events

All AEs will be followed until they have abated, or until a stable situation has been reached. Depending on the event, follow up may require additional tests or medical procedures as indicated, and/or referral to the general physician or a medical specialist. SAEs need to be reported until end of study within the Netherlands, as defined in the protocol. After termination of the trial, the investigator should assure that the subject is referred for medical follow-up, as appropriate.

9.4.1 Adverse event data collection

Signs and symptoms will be recorded in study diaries and reviewed during admission at the clinical trial research center, at all follow-up visits, and whenever a trial volunteer reports signs or symptoms to the trial physician between visits.

Solicited adverse events

After administration with mAb TB31F the following systemic signs and symptoms will be solicited until 28 days after infusion:

Fever, headache, myalgia, fatigue, chills, and rash. The time points that these symptoms are solicited is indicated in section 8.3.18.

After the administration of mAb TB31F the following local signs and symptoms will be solicited until 7 days after administration:

Pain at injection site and redness/swelling at injection site. The time points that these symptoms are solicited is indicated in section 8.3.18.

9.4.2 Monitoring periods for safety events

Adverse events will be collected during the study during the following periods:

- Solicited local AEs commonly associated with monoclonal antibody administration occurring through 7 days (day of TB31F administration and subsequent 6 days);
- Solicited general AEs commonly associated with monoclonal antibody administration and clinically significant hematological and biochemical laboratory abnormalities occurring through 28 days (day of TB31F administration and subsequent 27 days);
- Unsolicited AEs occurring through 84 days following TB31F administration (day of TB31F administration and subsequent 83 days);
- AEs (including SAEs) leading to withdrawal from the study during the entire study period post- mAb TB31F administration;
- SAEs during the entire study period post mAb TB31F administration;

9.4.3 Recording of adverse event data collection

Study staff will train subjects on use of memory aid booklets for self-assessment of solicited local and general adverse events through 7 days (day of mAb TB31F administration and subsequent 6 days) post- administration of study mAb TB31F; and for self-assessment of adverse events and concomitant medications until day 28. Study staff will review and discuss with the subject all recorded events to ensure appropriate documentation and scoring prior to transferring of the diary card record to the eCRF.

If known, the trial clinician will record the diagnosis (i.e., disease or syndrome) rather than component signs, symptoms and laboratory values. If the signs and symptoms are considered unrelated to an encountered syndrome or disease they should be recorded as individual AEs. If a primary AE is recorded, events occurring secondary to the primary event should be described in the narrative description of the case (e.g. primary AE = Orthostatic hypotension; secondary event may be fainting, head trauma, etc.). In case of hospitalizations for surgical or diagnostic procedures, the pre-existing condition should be recorded as the SAE, not the procedure itself.

All adverse events/reactions (solicited and unsolicited), noted by the investigators will be accurately documented in the case report form by the investigators. For each event/reaction the following details will be recorded:

1. Description of the event(s)/reactions(s)
2. Date and time of occurrence
3. Duration
4. Intensity
5. Relationship with the intervention
6. Action taken, including treatment
7. Outcome

In addition, symptoms will be ranked as (1) mild, (2) moderate, (3) or severe, depending on their intensity according to the following scale:

Mild (grade 1): awareness of symptoms that are easily tolerated and do not interfere with usual daily activity

Moderate (grade 2): discomfort that interferes with or limits usual daily activity

Severe (grade 3): disabling, with subsequent inability to perform usual daily activity, resulting in absence or required bed rest

If an adverse event changes in intensity during the specified reporting period, a new description of the adverse event will be added. Interrupted AEs are registered as one AE if the interruption is <24 hours. When an AE/SAE occurs, it is the responsibility of the investigators to review all documentation (e.g. hospital progress notes, laboratory, and diagnostics reports) related to the event. The investigators will then record all relevant information regarding an AE/SAE on the CRF or SAE Report Form, respectively.

The investigator will attempt to establish a diagnosis of the event based on signs, symptoms and/or other clinical information. In such cases, the diagnosis should be documented as the AE/SAE and not the individual signs/symptoms.

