2.3 Study Endpoints

Primary outcome endpoints:

- Number and severity of solicited local adverse events of all severities from first product administration through day 7;
- Number and severity of solicited general AEs and clinically significant hematological and biochemical laboratory abnormalities from first product administration through day 28;
- Number and severity of unsolicited adverse events from first product administration through end of study;
- Occurrence of serious adverse events from first product administration through end of study.

Secondary outcome endpoints

- Serum pharmacokinetics at each dose level through end of study by ELISA;
- Percentage of transmission reducing activity at different time points by SMFA.

Exploratory outcome endpoints

- Anti-drug antibody (ADA) levels in study subjects after receiving study product through end of study;
- An integrated population pharmacokinetic-pharmacodynamic model by Monte Carlo simulations.

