Escalation to the next higher dosage group will be dependent upon no safety signals arising as outlined in section 9.5.4 and will follow the same staggered algorithm as shown in figure 3. The SMC will review the safety data up to day 7 before proceeding to the next dosage group. The data to be reviewed before each dose escalation group includes the safety data (solicited and unsolicited AEs through day 7 post TB31F administration; see section 9.5.4) and clinically significant laboratory tests collected at 24 hours, 2 and 7 days following TB31F administration for all subjects in the specified dose group.

The decision to proceed at these defined time points to the next dosing group will be made by the study team upon the recommendation of the Safety Monitoring Committee (SMC) after reviewing the clinical and safety lab data available. Safety follow-up and collection of serum samples for pharmacokinetic and pharmacodynamic measurements will be done at following times: 0 hours, end

of infusion (EOI), 1, 3, 6 and 24 hours after product administration, and on days 2, 7, 14, 21, 28, 56 and 84 after product administration. Extra follow-up visits 4 and 10 days after administration for collection of serum/plasma for pharmacokinetic and pharmacodynamic measurements will be performed in group 5 (section 8.3.18). All subjects will be followed for approximately 84 days after mAb TB31F administration.

Table 1. Study groups

Study groups	Number of subjects	Single Dose	
		Mtb31F	Administration Route
Group 1	5	0.1 mg/kg	intravenous
Group 2	5	1 mg/kg	intravenous
Group 3	5	3 mg/kg	intravenous
Group 4	5	10 mg/kg	intravenous
Group 5	5	100 mg	subcutaneous

[figure not shown]

Figure 3 – Staggered dosing trial design for monoclonal antibody TB31F administration

For group 1, all subjects will receive a single dose of TB31F with a window of at least 48 hours. For groups 2-5, subject 1 and subject 2 will receive a single dose of TB31F with a window of at least 48 hours. Subjects 3, 4 and 5 of the same group will receive the same dose of mAb TB31F minimally 48 hours after subject 2. Escalation to the next dosage group will occur if no Group Holding Rules are met and upon review by the SMC.

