5.2 Use of co-intervention (if applicable)

In order to be eligible for the study, subjects must abide to the inclusion and exclusion criteria as described in section 3.2 and 3.3 of this protocol. Therefore:

- subjects may not chronically use i) immunosuppressive drugs, ii) antibiotics, iii) or other immune modifying drugs within three months prior to study onset (inhaled and topical

corticosteroids and oral antihistamines exempted);

- male and female subjects must use continuous adequate contraception until 2 months after study completion. Females may not breastfeed from 30 days prior to mAb administration until 2 months after completion of the study;
- subjects must be reachable by phone (24/7) throughout the entire study period from day -1 until day +84;
- subjects will remain within reasonable travelling distance from the study center from day -1 until day +7 after mAb TB31F administration;
- subject must refrain from blood donation to Sanquin following current Sanquin guidelines;
- subjects may not receive any immunoglobulin and/or any blood products within three months preceding the first dose of study mAb or throughout the study, with the exception of TB31F;
- subjects may not participate in any other trials during the study period;
- subjects must always contact the trial physician if they experience any medical complaint throughout the entire study period;
- subjects may be required to respond to standardized Radboudumc-wide COVID-19 measures e.g. a questionnaire prior to study visits and/or undergo presumptive (e.g. at inclusion visit) and/or symptom-driven COVID-19 testing, e.g. a nasopharynx/throat swab for SARS-CoV2 PCR, in accordance with current Radboudumc-wide or MC-specific guidelines.

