- mAb TB31F will be administered by slow intravenous drip (see Appendix 2 for infusion rates) in group 1 up till group 4. The infusion rate will be reduced by 50% for mild reactions; and terminated for severe infusion reactions. MAb TB31F will be administered subcutaneously by slow injection in group 5, divided equally between two injection sites (1mL per site). Subjects will be observed directly for at least 60 minutes after the infusion. One intravenous dwelling catheter may be removed following drug product administration.
- Collection of serum/plasma for pharmacokinetic and pharmacodynamic measurements will be done at the following time points: 0 hours, EOI and 1, 3, and 6 hours after product administration. Subjects may leave the Medium Care Unit after 6 hours and return the next day to the clinical research center for the 24-hour blood sampling time point.
- Vital signs, adverse events (solicited and unsolicited) and blood will be collected at each time point as indicated in section 8.3.18.
- A list of solicited local and systemic symptoms will be reviewed with the subject at 0, EOI, 1, 3 and 6 hours (day 1) and 24 hours (day 2). If the occurrence of an adverse event or use of medication is confirmed by the study physician, it is recorded in the clinical trial database.

- After leaving the hospital, subjects will be asked to examine the site of infusion and record local signs and symptoms for seven days including bruising, erythema, swelling or induration. Subjects will be asked to measure their oral temperature daily until day 7. Subjects will be asked to record any AEs in the memory aid booklet until day 84. At the end of the study, the memory aid will be collected and kept as source data with the subject's study file.

All inoculations are performed by a trained nurse under the supervision of one of the clinical investigators. Another clinical investigator will be on call in case of emergency. Local hospital procedures will be followed. Study subjects will be monitored at the Medium Care Unit on the day of TB31F administration. The venous catheter will be removed at the end of visit 3 (day of product administration) and subjects will be discharged from the Medium Care Unit. Follow-up visits will take place as described in section 8.3.18.

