8.3.5 Follow-up after mAb TB31F administration (visits 4-12)

Follow-up visits will be carried out on an outpatient basis at the study center. Subject will be asked to examine the site of injection and record local signs and symptoms in their memory aid booklet (including bruising, erythema, swelling or induration) for seven days after injection as well as systemic symptoms throughout day 28. Subjects will also be asked to measure their body temperature in the mornings for 6 consecutive days after mAb TB31F administration. The subject diary will be reviewed at each study visit and used as a base for discussion of possible local and systemic adverse events or medication use. If the occurrence of an adverse event or use of medication is confirmed by the study physician, it is recorded in the clinical trial database. At the end of the study, the diary will be collected and kept as source data with the subject's study file. Follow-up visits *not* requiring blood collection for safety endpoints may be carried out by telephone, or at home, instead of at the clinical research center for subjects with suspected or confirmed SARS-CoV2 infection, until such time as they are considered no longer (potentially) contagious in accordance with current Radboudumc-wide guidelines. In such cases, it may not be possible to obtain blood samples for non-safety endpoints (PK, ADA & SMFA).

During the study period subjects will be instructed to call the trial physicians at any time if they experience severe symptoms or symptoms related to COVID-19. If clinically significant abnormalities are identified during the study, subjects may be asked to return to the study site for further evaluation, including clinical evaluation and repeat laboratory testing as warranted. The trial physician can decide to initiate any additional diagnostics (including safety laboratory evaluations) at all times. For unexpected laboratory abnormalities, the laboratory test will be repeated. If there is any ambiguity regarding the decision to include or exclude a volunteer, a trial physician will discuss the case with the local safety monitor.

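### Protocol 9.4.3 ends diary recording of adverse events at day 28 and 8.3.4 at day 84, while unsolicited events are a primary endpoint to day 84

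*Protocol*

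**What the plan says.** Protocol 2.3 lists as a primary endpoint "Number and severity of unsolicited adverse events from first product administration through end of study". Section 9.4.2 sets the same window at 84 days, counting the day of administration. The SAP's safety outcome measures also run to end of study for this outcome.

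Three protocol sections say how long the subject keeps the diary, which the protocol also calls the memory aid:

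- 8.3.4: "Subjects will be asked to record any AEs in the memory aid booklet until day 84". The booklet is collected at the end of the study.
- 8.3.5: local signs "for seven days after injection as well as systemic symptoms throughout day 28". It gives no diary period for other events.
- 9.4.3: subjects are trained to use it for solicited local and general events through 7 days, and "for self-assessment of adverse events and concomitant medications until day 28".

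The diary is a working instrument. Under 8.3.5, "The subject diary will be reviewed at each study visit and used as a base for discussion of possible local and systemic adverse events"; under 9.4.3 its entries are reviewed and transferred to the eCRF; and 12.1.1 makes it source data. Section 3 places the later follow-up visits after the first 24 hours "and on days 2, 7, 14, 21, 28, 56 and 84 after product administration".

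**The concern.** Sections 8.3.4 and 9.4.3 cannot both be followed. Under 9.4.3, the way unsolicited events are ascertained changes at day 28, part of the way through a primary endpoint's window. Before day 28 there is a diary and visits are close together. After it there is no diary and visits are four weeks apart.

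For each event, 9.4.3 requires date and time, duration and intensity, and a gap of under 24 hours decides whether two episodes count as one. Those details are hard to rebuild weeks later without notes. Mild, short events and medication use are the most likely to be lost. A day-84 count could then look quieter after day 28 partly because the method changed.

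The same sentence of 9.4.3 has a second mismatch. It names 7 days for solicited general events, whereas 9.4.1 and 9.4.2 solicit them for 28 days. Its day-28 clause on adverse events may be meant to cover the remainder, but it does not say so.

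**Working it through.** **1. The plan's own safety figure.** Protocol 4.4 gives, for n = 20, a 90% chance of at least one event at a true rate of 10.87% and a 90% chance of none at 0.52%.

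- 1 − (1 − 0.1087)^20 = 0.8999
- (1 − 0.0052)^20 = 0.9010

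Both reproduce. They take it for granted that an event which occurs is recorded. Nothing here disputes or changes them.

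**2. The periods side by side.**

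| Protocol section | Local solicited | General solicited | Unsolicited or any AE | Concomitant medication |
|---|---|---|---|---|
| 9.4.1, 9.4.2 (collection window) | 7 days | 28 days | 84 days | not covered |
| 8.3.4 (diary) | 7 days | within any AE, to day 84 | day 84 | not stated |
| 8.3.5 (diary) | 7 days | day 28 | not stated | no end date |
| 9.4.3 (diary training) | 7 days | 7 days as written | day 28 | day 28 |

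Only the local solicited period agrees throughout. For unsolicited events only 8.3.4 matches the endpoint. For medication, 9.4.3 is the only section that gives a diary end date.

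**3. Share of the window without a diary if 9.4.3 is followed.** With the 84-day window of 9.4.2, (84 − 28)/84 = 56/84 = 66.7%. Counting days 0 to 84 inclusively gives 56/85 = 65.9%. Either way it is about two thirds.

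**4. Scheduled contacts in that share.** After day 28 the visits are days 56 and 84, so there are two. The nominal interval before each is 28 days. With the allowances in Table 3 (day 28 ± 2, days 56 and 84 ± 5), the longest intervals are:

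- 61 − 26 = 35 days
- 89 − 51 = 38 days

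**5. Can the loss be sized?** The fraction of all unsolicited events lost equals the share of events that occur after day 28 times the share of those that are missed. The documents give neither term. Any percentage would only restate the two values put in.

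**The case against.** The strongest reply is that the design is clear and 9.4.3 is a drafting slip. Section 8.3.4 is the instruction for what subjects do after leaving hospital. The booklet is collected at study end, 8.3.5 and 9.4.1 have the diary reviewed at every follow-up visit, and the schedule in 8.3.18 carries unsolicited events over days 0-84. This stands as evidence of intent. It does not settle which instruction was carried out: 9.4.3 is the section on recording adverse event data and says what subjects are trained to do, 8.3.5 names nothing beyond day 28, and 8.4.1 allows that the memory aid may no longer be in use when a subject withdraws.

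A reader might infer that late events rest on recall alone at two visits. The documents do not support that. Under 5.2, "subjects must always contact the trial physician if they experience any medical complaint throughout the entire study period"; 9.2.1 records all spontaneous reports; 9.4.1 reviews complaints made between visits; and 8.3.2 has medication recorded at all visits. This softens the point considerably. It is weakest for mild events, because 8.3.5 instructs subjects to call about severe symptoms or symptoms related to COVID-19.

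Three further readings go beyond the documents:

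- **A numerical undercount.** It would need an assumed miss rate and an assumed spread of events over time.
- **Late immune reactions missed.** Section 13.1 names serum sickness and anti-idiotypic antibodies as risks of such products but gives no timing.
- **Bias between dose groups, or in a planned time trend.** The same text applies to all five groups, and neither document plans an analysis of unsolicited events over time. The exact-interval tabulation of unsolicited events in protocol 10.1 stops at day 28, and escalation uses day-7 data. Neither depends on the later diary.

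**Conclusion.** The contradiction is real and stands in current text. It is more than clerical, because the diary is the basis for adverse event discussion at visits and is source data for a primary endpoint.

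If 9.4.3 is followed, unsolicited events in the last 56 of 84 days (66.7%) are captured without a diary, through two scheduled visits plus complaints reported in between. Mild, short events and concomitant medication could then be recorded less completely than before day 28. Serious and severe events are least exposed. What is affected is the descriptive count of unsolicited events to day 84.

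This rests on one condition that the documents do not settle: that training and the booklet followed 9.4.3 and not 8.3.4. If they followed 8.3.4, the unsolicited-event diary covers the whole window and only the wording needs repair. The size of any loss cannot be derived from the documents.

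**What to change.** State one set of diary periods in 8.3.4, 8.3.5 and 9.4.3, matched to the endpoints:

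- local solicited events to day 7
- general solicited events to day 28
- unsolicited events and concomitant medication to day 84

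Align the training material and the booklet. Changing the day-28 phrase in 9.4.3 alone is not enough, because it would leave 8.3.5 and the 7-day wording for general events as they are.

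Protocol 13.2 says that groups 1-4 have already been dosed. For subjects already followed, the report should state which diary period was used. If it was day 28, it should present unsolicited events separately for days 0-28 and after day 28, so that a quieter later period is not read as a safety finding without regard to the change in method.

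The cost is a few phrases of text, matching training material, and slightly more diary burden. The booklet is already collected at the end of the study.

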9.2 AEs, SAEs and SUSARs

9.2.1 Adverse events (AEs)

Adverse events are defined as any undesirable experience occurring to a subject during the study, whether or not considered related to the investigational product. All adverse events reported spontaneously by the subject or observed by the investigator or his staff will be recorded. Abnormal laboratory findings (e.g. clinical chemistry or hematology) or other abnormal assessments that are judged by the investigator to be clinically significant will be recorded as AEs (or SAEs if they meet the definition). The investigator will exercise his or her medical and scientific judgment in deciding whether an abnormal laboratory finding or any other abnormal assessment is clinically significant. If there are any severe complaints, the volunteer will be evaluated immediately by a qualified clinician using the appropriate clinical assessments according to standard hospital care.

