#### Safety outcome measures:

1. Number and severity of solicited local adverse events from the moment of first product administration through day 7
2. Number and severity of solicited general AEs from the moment of first product administration through day 28
3. Number and severity of clinically significant hematological and biochemical laboratory abnormalities from the moment of first product administration through day 28
4. Number and severity of unsolicited adverse events from first product administration through end of study
5. Number of serious adverse events from first product administration through end of study

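### The rule to record a diagnosis instead of its symptoms has no exception for solicited AEs, so the solicited-symptom rows of the primary endpoint can be understated

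*Protocol*

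**What the plan says.** **Recording rule.** Protocol section 9.4.3 instructs that, if the diagnosis is known, "the trial clinician will record the diagnosis (i.e., disease or syndrome) rather than component signs, symptoms and laboratory values". Symptoms stay separate only in one case: "If the signs and symptoms are considered unrelated to an encountered syndrome or disease they should be recorded as individual AEs". Later in the section the investigator is told to try to reach a diagnosis, and the rule is repeated: "In such cases, the diagnosis should be documented as the AE/SAE and not the individual signs/symptoms". The same section states that its case-report-form recording covers solicited and unsolicited events together. It names no exception for the solicited list.

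**Endpoint.** The protocol Summary defines the primary endpoint by the presence of fever, headache, myalgia, fatigue, chills and rash, plus local pain, redness and swelling. Section 2.3 asks for number and severity, and section 9.4.1 gives the solicited list. The SAP repeats this under its safety outcome measures: "Number and severity of solicited general AEs from the moment of first product administration through day 28". None of these texts makes the count depend on cause or diagnosis.

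**Analysis.** Under its safety outcome analyses, the SAP tabulates subjects by solicited AE type and grade, and adds rows for any solicited local, any solicited general and any solicited AE. Unsolicited events go to a separate description by ICD-10 category. The SAP has no step that returns a symptom absorbed into a diagnosis to its solicited row.

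**The concern.** Recording the diagnosis is sensible for unsolicited events, because it avoids listing one illness several times. Solicited events serve a different purpose. They are a fixed list, asked of everyone over a fixed period and graded on a fixed scale, so that rates can be compared across dose groups. A rule that removes a listed symptom once it is explained works against that purpose.

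The rule acts when symptoms cluster into something recognisable, and the protocol foresees such diagnoses. Section 5.3 plans for infusion-related reactions, section 13.1 mentions acute anaphylaxis and serum sickness with antibodies in general, and section 5.2 provides symptom-driven COVID-19 testing, where a positive result would supply a known diagnosis. Each could absorb several solicited symptoms within the 28-day window.

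At stake is the accuracy of the symptom-level reactogenicity rows. These are part of the primary endpoint of a first-in-human study.

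**Working it through.** **1. The plan's own figure.** Protocol section 4.4 and the SAP sample-size section state, for n = 20, a 90% chance of at least one event at a true rate of 10.87%, and a 90% chance of none at 0.52%.

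- 1 − (1 − 0.1087)^20 = 0.8999
- (1 − 0.0052)^20 = 0.9010

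Both reproduce. The point does not dispute them; it turns on the text of the recording rule.

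**2. One subject followed through the rules.** Take a hypothetical subject in a group of five with fever, chills, headache and myalgia on the dosing day, diagnosed as an infusion-related reaction. Assume no other solicited symptom in this subject and none of these symptoms in the other four.

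| Row | Symptoms entered individually | 9.4.3 as written |
|---|---|---|
| Fever, chills, headache, myalgia (each) | 1/5 | 0/5 |
| SAP: any solicited general AE | 1/5 | 0/5 |
| SAP: unsolicited, by ICD-10 | diagnosis only if entered in addition | 1 event |
| Protocol 10.1: any general AE, solicited and unsolicited | 1/5 | 1/5 |

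The first two rows change and the last does not.

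**3. Size per affected subject.** Section 10.1 specifies exact 95% intervals. For x of n these are the Clopper-Pearson limits: lower = the 0.025 quantile of Beta(x, n − x + 1), upper = the 0.975 quantile of Beta(x + 1, n − x).

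- 1/5 = 20%, interval 0.5 to 71.6%
- 0/5 = 0%, interval 0 to 52.2%; the upper limit is 1 − 0.025^(1/5) = 0.522
- Change in a group row: 1/5 = 20 percentage points
- Change in the SAP's column for all 25 subjects: 1/25 = 4 percentage points

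**4. Frequency.** The documents do not say how often a diagnosis would replace solicited symptoms. For illustration only, let f be the assumed share of subjects with a given solicited symptom whose symptom is recorded only as a diagnosis. The chance that the solicited row shows at least one subject, at a true rate of 10.87%, is 1 − [1 − 0.1087(1 − f)]^n.

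| f (assumed) | n = 20 | n = 5 |
|---|---|---|
| 0 | 90.0% | 43.8% |
| 10% | 87.2% | 40.2% |
| 25% | 81.7% | 34.6% |
| 50% | 67.3% | 24.4% |

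The table shows how sensitive the row is to f. It does not estimate the loss.

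**The case against.** **A solicited pathway exists.** Section 8.3.4 has a list of solicited symptoms reviewed with the subject at set times. Section 9.4.3 has diary records checked with the subject and then transferred to the eCRF. The diagnosis rule is a separate paragraph and applies only when a diagnosis is known; its worked example contains no solicited symptom. The eCRF may well have a solicited-symptom page. This stands as a reason not to claim that symptoms will certainly drop out. It does not create an exception: no such page is described, and the diary also carries unsolicited events.

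**Individual symptoms have been reported.** Section 13.2 reports grade 1 or 2 fatigue in 12 of 20 subjects and grade 1 local events in 2 of 20. The fatigue is counted although the premedication is offered as an explanation. That shows isolated symptoms are captured, but does not test symptoms that form a diagnosed syndrome. It does mean that a subject with separate dosing-day fatigue would still count in the any-solicited rows.

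**The event stays visible.** This stands. Section 10.1 also tabulates general AEs, solicited and unsolicited together, and any AE in the solicited period, with the same for grade 3. Section 9.5.3 puts unsolicited AEs by severity and relatedness before the safety committee.

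**Stronger readings that the documents do not support.**

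- *High fever would vanish from the grade 3 data.* Table A3 also grades fever as a vital sign, and section 10.1 lists clinically significant out-of-range vital signs. That a replacing diagnosis would carry a lower grade is inference.
- *A holding rule would be missed.* The rule in section 9.5.4 covers any related grade 3 event, not only solicited ones, and a hold can be called on advice at any time. An effect is speculative.
- *Physician confirmation is a second filter.* Section 8.3.5 says that an event, if it "is confirmed by the study physician, it is recorded in the clinical trial database", whereas section 9.2.1 says "All adverse events reported spontaneously by the subject or observed by the investigator or his staff will be recorded". Confirmation can be by history and diary discussion, which 8.3.5 and 9.4.3 describe, so a resolved headache need not be lost.

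**Conclusion.** The point holds for the solicited rows. The recording rule and the primary endpoint conflict as written: one withholds component symptoms when a diagnosis is known, and the other counts those symptoms whatever their cause. If the rule is followed literally, the individual solicited-symptom rows and the SAP's solicited-only summary rows are understated, along with the grades they carry. The combined rows in section 10.1 and the safety committee's reports still include the event.

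Each affected subject costs 20 percentage points in a group row, provided the symptom occurred only within the diagnosed condition. The total effect cannot be estimated from the documents, and it is zero if no diagnosis is made or if the eCRF already captures solicited symptoms separately. The safety analyses are mainly descriptive, so what suffers is the reported reactogenicity profile, not a powered test. The correction should be made, but nothing here shows that a safety signal would be hidden.

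**What to change.** Add to section 9.4.3, and repeat in the SAP's safety outcome analyses:

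- Solicited signs and symptoms within their window are always entered individually, each with its own Table A1 or A2 grade.
- Any unifying diagnosis is entered in addition and linked to them, so that the unsolicited table can be shown with and without it.
- The rule to record the diagnosis instead of its symptoms applies to unsolicited AEs only.

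Rash is on the solicited list, but I find no row for it in Table A2, so the text should name the scale used for rash. For subjects already followed, the diaries are kept as source data, so any diagnosis entered within the solicited window can be checked against them before database lock.

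The cost is a few sentences in the protocol, SAP and eCRF guidance, some more AE lines and slightly higher solicited rates. No new visits or data collection are needed. If the eCRF already works this way, the change only writes down current practice.
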